AURORA HEALTH CARE, INC.

PROTOCOL TITLE: Pilot study for the efficacy and tolerability of Senokot-S[®] in the treatment of diabetic gastroparesis

PRINCIPAL INVESTIGATOR:

[name] Hospitalist [name] [contact] [contact] Email: [contact]

INVESTIGATORS AND KEY PERSONNEL:[name], [name], [name]

This protocol was designed and developed by Aurora Healthcare, Inc. It is intended to be used only in conjunction with institution-specific IRB approval for study entry.

I. Background and Significance

Diabetic gastroparesis can be a difficult-to-treat complication of longstanding diabetes that can significantly compromise quality of life in those affected. Today there is only one medication approved by the FDA for the indication of diabetic gastroparesis and it has received a black box warning due to potential for severe neurological side effects. There are other medications that have found some success in the treatment of diabetic gastroparesis, but they also have the potential for serious side effects, and some are only available through a special use program.¹

II. Specific Aim

The aim of the study is to evaluate the efficacy of the stimulant laxative Senokot-S[®] for the treatment of diabetic gastroparesis. Senokot-S, and its metabolites, are thought to produce peristalsis, drive intra-luminal fluid and electrolyte shifts, and have an irritant effect on the gut mucosa^{2,3}. These complex physiologic mechanisms appear may sufficiently promote stomach emptying, and thereby reduce or eliminate the severity of gastroparesis symptoms. In this open label study, participants will be randomized into high and low dose groups to assess for ideal dosing and tolerability. It is the overall goal of this study to select the most promising dose-strength for the treatment of mild through severe gastroparesis.

(c) Study End Points

- a. Primary Endpoint
 - i. Modified GCSI-DD: Subjects will complete the modified Gastroparesis Cardinal Symptom Index-Daily Diary (mGCSI-DD)^{4,5}. The mGCSI-DD is a validated patient reported outcome (PRO) instrument with excellent testretest reliability, and will be used as the primary instrument to assess for efficacy in this study.

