 - ii. Questions on the mGCSI-DD are a 6-point Likert scale from 0 (none) to very severe (5) that address: nausea, retching, vomiting, stomach fullness, ability to finish a normal-sized meal, feeling excessively full after meals, loss of appetite, bloating, external assessment of stomach size, upper ab-dominal pain or discomfort.
- b. Secondary Endpoint
 - i. Breakthrough medication use: Defined as the change in the frequency of use of breakthrough medication, which is the medication that has been previously prescribed on an as-needed basis to manage symptoms.

Any change in frequency of use of breakthrough medications will be used as a secondary endpoint to assess for efficacy in the study.

 Bowel habits: Subjects will self report bowel habits during the baseline week and through the study period on the same questionnaire form. Since Senokot-S functions primarily as a mild bowel stimulant any significant change in bowel habits will help to assess for tolerability in this study.

IV. Study Design

The Phase II study design will be an open label, pre- and post-treatment assessment, prospective study. Sixty (60) study participants will be recruited over a 5-month period at a single site. Participants will be randomized into two treatment groups, a high- and low-dose, and will take medication dosed orally, twice daily or once daily at night.

V. Experimental Design, Methods, and Study Procedures

- **a.** Initial Identification of Potential Study Subjects Gastroenterologists who have agreed to refer their patient with diabetic gastroparesis for this study will make the initial contact with those patient (study inclusion/exclusion criteria will be provided to these physicians for ready reference). If the patient is interested in participating in the study the gastroenterologists will secure the patient's verbal permission to provide their name and contact information (phone or e-mail) to [name] or another member of the study team. The study team member will contact the patient and arrange a time to meet with them to explain the study and to answer any questions the potential subject may have.

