- b. Screening Visit The screening visit will include reviewing the participants' complete medical history after reviewing and obtaining informed consent. Data from the participant's medical history will be abstracted from the electronic medical record (EMR) and will be securely stored with other study-related data. Participants will be given the mGCSI-DD questionnaire and instructed on its use. At this visit participants will start recording their week of baseline scores by filling out a separate mGCSI-DD questionnaire and Breakthrough Medication Use and Bowel Habits documentation form daily.
- c. Visit 1 will occur 1 week after the screening visit. Participants will return with their mGCSI-DD baseline week of scores. They will be sequentially randomized (1:1) into either the high (8.6/50mg of senna/docusate taken by mouth twice daily) or low (8.6/50mg of senna/docusate taken by mouth once every night) dose study group. To reduce potential subject bias and placebo effect, participants will not be informed as to which dose of study medication they are randomized. They will be given their study medication and their 28-day mGCSI-DD questionnaire sheets, along with a pre-printed return envelope for use after completing their month of treatment in the study. They will be instructed to decrease use of any previously prescribed breakthrough medication as can safely be tolerated. Examples of these medication may include prokinetics such as Reglan (metoclopramide), erythromycin, or domperidone; anti-emtics such as Zofran (ondansetron), or Compazine (prochloperazine); or analgesics such as tramadol,

hydrocodone, or oxycodone. They will also be instructed to resume any breakthrough medication use as previously prescribed at the completion of the study and to continue routine follow ups with their care providers.

Subjects will be instructed to immediately contact the Principal Investigator if they experience episodes of significant diarrhea or rectal bleeding.

Participants may be notified by phone at the end of their study period to verify data or request missing data.

VI. Risks

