Senokot-S side effects. Known side effects of Senokot-S include diarrhea, nausea or vomiting, stomach pain, rectal bleeding, gas, abdominal bloating, and potential for allergic reaction such as skin rash. There have been safety concerns in the past about potential complications from long term use of stimulant laxatives like Senokot-S, such as cathartic colon, increased incidence of colorectal cancer, and liver disease. Several recent studies and reviews refute those previous conclusions and suggest long-term use of mild stimulant laxatives is likely safe when needed^{3,6,7}. Senokot-S is listed as pregnancy category C by the FDA. Women with child bearing potential will be required to use an effective form of birth control while participating in this study.

Ineffective treatment of diabetic gastroparesis. Since this medication has not yet been studied in the treatment of diabetic gastroparesis it is possible that symptoms of the disorder may worsen. The common symptoms of diabetic gastroparesis include nausea, vomiting, postprandial fullness, early satiety, and abdominal pain.

Loss of confidentiality. It is expected that this risk will be low because of numerous safeguards that will be in place, including standard data management procedures with Aurora Health Care.

VII. Benefits

A successful outcome in the proposed study will have immediate implications by reducing the symptoms of diabetic gastroparesis. Such a result will address the significant unmet need by providing a safe, inexpensive pharmacological therapy for a difficult to treat chronic disorder. These findings would allow patients to reduce or eliminate intake of the only FDA-approved therapeutic medication, Reglan[®], which has a black box warning and unfavorable side-effect profile. These known potential benefits are highly likely to outweigh the potential risks of the intervention in this study.

VIII. Study Population

Inclusion Criteria:

- Age 18-75 years, male and non-pregnant, non-lactating females
- Diagnosis of type 1 or type 2 diabetes mellitus
- Clinical diagnosis of diabetic gastroparesis

Exclusion Criteria:

- Diagnosed idiopathic gastroparesis
- A history or inflammatory bowel disease, such as Crohn's disease or ulcerative colitis
- A history of bowel obstruction, current unexplained abdominal pain, or undiagnosed rectal bleeding
- Gastrointestinal cancer
- Any active cancer
- Prior gastric surgery
- End-stage heart disease, liver disease, lung disease

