- Known or suspected drug abuse
- Any condition requiring use of daily narcotics
- Concurrent usage of mineral oil or products containing mineral oil
- Current or recent (within the last 3 months) usage of Senokot-S, docusate or senna

IX. Recruitment and Screening

Recruitment will occur through care provider referrals. Clinicians will be notified of the study through paper advertisement and posters. Initial screening will be done over the phone or through e-mail at the time of referral and will include a medical record review. Final screening and informed consent will be completed during the formal in person screening visit between the participant and research staff and is expected to take about one to two hours.

X. Privacy Plan

Patients will initially be notified of the potential to be in a research study by a current caregiver. If the patient is agreeable to consideration for the study the research team will be contacted by phone or through e-mail by the clinician with the patient's contact information. The patient will then be contacted by a member of the research team via an institution-based phone or EMR e-mail (based on the patient's preference) for initial screening and to set up a clinic visit for final screening and informed consent.

XI. Data Collection

The data to be collected will include a complete medical history of the participant, mGCSI-DD score forms, medication usage and bowel habits forms. Data will not be shared with any outside institutions.

This research study plans to store and manage the subject lists, demographic information, validated questionnaire, study and breakthrough medication use, and bowel habits datasets in REDCap Cloud, a secure electronic data capture application that is based on Vanderbilt University's REDCap application. Flexible for a variety of types of research, REDCap Cloud provides an intuitive data-entry interface for end users into study-specific data collection forms associated with study events. The application includes real time validation rules and query management, audit trails, and the automated export of study data into statistical programs. The REDCap Cloud platform is compliant with GCP predicate rule requirements and US FDA 21 CFR Part 11 pertaining to the use of electronic records and signatures. Aurora Health Care, Inc. has executed an agreement for use of the application with nearly all research studies conducted at Aurora.

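### Dose tolerability is a stated aim, but its only named measure has no direction or threshold, and the listed data include no adverse-event form or reason for stopping

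*Combined protocol and SAP*

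**What the plan says.** - **Purpose.** Section II (Specific Aim) states that "participants will be randomized into high and low dose groups to assess for ideal dosing and tolerability". The overall goal given there is to choose between the two dose strengths, so a comparison of tolerability between arms belongs to the aim.
- **Measure.** The Secondary Endpoint section says of bowel habits that "any significant change in bowel habits will help to assess for tolerability in this study". The same sentence describes the drug as mainly a mild bowel stimulant. Recording is by self-report: "Subjects will self report bowel habits during the baseline week and through the study period on the same questionnaire form".
- **Known harms.** Section VI: "Known side effects of Senokot-S include diarrhea, nausea or vomiting, stomach pain, rectal bleeding, gas, abdominal bloating", followed by possible allergic reaction such as rash.
- **Data listed.** Section XI: "The data to be collected will include a complete medical history of the participant, mGCSI-DD score forms, medication usage and bowel habits forms". The stored datasets also cover "study and breakthrough medication use, and bowel habits datasets in REDCap Cloud". Neither list names an adverse-event form, a severity grade or a reason for stopping.
- **Other safety provisions.** Section V.c: "Subjects will be instructed to immediately contact the Principal Investigator if they experience episodes of significant diarrhea or rectal bleeding". Section XIII gives safety monitoring to the research office and principal investigator, and lets participants leave at any time for any reason. Section XIV requires reporting under the IRB's own procedures, which are not part of the document.
- **Analysis.** Section XII names appropriate parametric or non-parametric tests at alpha 0.05. It specifies no tolerability analysis.

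**The concern.** A change in bowel habits is what this drug is meant to cause. A participant whose constipation eases and a participant who develops diarrhoea have both changed, and only the second is a tolerability problem. An outcome with no direction and no threshold does not separate them. The choice of how to do so would be left until the data are in hand, in a study described as open label.

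The second gap is capture. Rash and gas are acknowledged side effects but are not mGCSI-DD items, and no listed form is said to record them. A participant may stop because of a side effect without the reason being recorded. Such information is hard to recover once the 28 treatment days are over. What is at stake is the tolerability half of the dose choice.

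**Working it through.** The plan gives no event rate, power or sample-size basis, so there is no figure of its own to reproduce. The check has two parts.

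**1. Each known effect set against the place where it would be recorded**

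| Effect | Where the plan would record it | Defined comparison by dose? |
|---|---|---|
| Diarrhoea | Bowel-habits form (items not shown); call to investigator if significant | No |
| Rectal bleeding | Call to investigator | No |
| Nausea, vomiting, bloating, upper abdominal pain | mGCSI-DD items, which are also the primary efficacy instrument | Not as tolerability |
| Gas, rash | No listed form is said to record them | No |
| Stopping because of a side effect | Study-medication use is stored; the reason is not listed | No |

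A related point needs reconciling. The endpoint section has bowel habits reported through the study period, and section V.b has the form completed daily in the baseline week. The materials handed out at Visit 1 (section V.c) are the medication, the 28-day mGCSI-DD sheets and an envelope. The bowel-habits form is not mentioned there.

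**2. What the missing direction could cost (illustration only)**

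Inputs from the plan: 60 participants (section IV) randomised 1:1 (section V.c), so 60/2 = 30 per arm; alpha 0.05 (section XII). Two-sided testing is assumed because the plan does not say. All event rates are assumptions, and so is the binary any-change outcome, which is one possible reading of the sentence.

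Method: for each pair of counts (x, y), compute z = (x/30 − y/30) / √[p̄(1 − p̄)(2/30)] with p̄ = (x + y)/60. Power is the sum of the binomial probabilities of all pairs with |z| > 1.96. The any-change rate is the diarrhoea rate plus the relief rate, taking the two as mutually exclusive.

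| Diarrhoea, low v high | Relief, low v high | Any change, low v high | Power, diarrhoea alone | Power, any change |
|---|---|---|---|---|
| 5% v 30% | 20% v 20% | 25% v 50% | 0.778 | 0.516 |
| 5% v 30% | 30% v 30% | 35% v 60% | 0.778 | 0.505 |
| 5% v 30% | 40% v 40% | 45% v 70% | 0.778 | 0.507 |
| 5% v 30% | 40% v 15% | 45% v 45% | 0.778 | 0.051 |
| 5% v 30% | 20% v 40% | 25% v 70% | 0.778 | 0.96 |
| 10% v 30% | 30% v 30% | 40% v 60% | 0.50 | 0.35 |

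Equal relief in both arms is enough to take power from about 78% to about 51%. The fourth row is a worst case, with relief rates chosen so that the arms match. The fifth row shows the opposite error: of the 45-point gap, 70 − 25, 20 points are benefit.

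**What 30 per arm can show even with a directional outcome.** At 10% v 20% power is only 0.19. At 10% v 30% the 95% CI half-width is about 1.96 × √(0.10×0.90/30 + 0.30×0.70/30) = 1.96 × √(0.003 + 0.007) = 0.196, so a 20-point difference would carry an interval of roughly 0 to 40 points. If no event of a given kind is seen in an arm, the one-sided 95% upper limit is 1 − 0.05^(1/30) = 9.5%. That bound is available only if events are recorded systematically.

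**The case against.** A reader might infer that the plan scores relief of constipation and new diarrhoea alike. It does not say so; it is silent on direction. The bowel-habits form is not reproduced, and if it records frequency or consistency, direction against the baseline week could be recovered. That stands. It also means that the trial may be able to answer the question, and that the defect is the lack of a stated definition.

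A reader might also infer that bowel habits are the sole basis for tolerability, or that no adverse events are recorded at all. Neither is supported. The endpoint sentence says the measure will help, and the data list says what will be included; neither wording is exclusive. Investigator contact, safety monitoring and IRB reporting are all provided for, and events reported that way could be tabulated by arm. Study-medication use is stored and is a partial proxy for tolerability. Item-level mGCSI-DD worsening is also available, since the plan fixes no total-score rule. What remains is that none of these provisions is tied to systematic capture or to a between-dose comparison, and that the contact instruction names only significant diarrhoea and rectal bleeding.

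The power figures depend on assumed rates, and the pattern of relief can push them either way. This is also a pilot with efficacy as its primary endpoint, and part of the weakness comes from 30 per arm rather than from wording. Those points limit the size of the concern. They do not supply the missing definition or the missing fields.

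**Conclusion.** The point holds in this form: the plan randomises partly to compare tolerability, yet it does not define how that comparison will be made. Its one named measure has no direction or threshold. Rash, gas and side-effect-related stopping are not covered by any listed systematic record by arm; for gas this assumes that the unseen bowel-habits form does not ask about it.

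The size cannot be fixed from the document. Under the assumed rates above, equal relief costs roughly 27 points of power (78% to 51%), while unequal relief could hide the diarrhoea difference or exaggerate it. The stronger conclusion, that any tolerability result would be uninterpretable, is not supported, because direction and some side effects may be recoverable from the forms. This is a cheap improvement that should be made before participants start treatment.

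**What to change.** 1. Replace the bowel-habits sentence with a directional outcome: the proportion of participants, and the mean days per week, with new or worsened loose stools or diarrhoea relative to their own baseline week. State the threshold. Report relief of constipation separately, as a benefit.
2. Confirm that the bowel-habits form records frequency and consistency, and that it is supplied for all 28 treatment days. Reconcile section V.c with the endpoint section on this.
3. Add an adverse-event line to the daily form, and a log in REDCap Cloud for adverse events and reasons for stopping. Enter the telephone reports to the investigator in the same log.
4. In section XII, commit to reporting each of these outcomes by arm with a difference and 95% CI, described as estimation rather than a powered test.
5. Add a supporting table, from data already collected, of item-level mGCSI-DD worsening by arm for nausea, vomiting, bloating and upper abdominal pain. These items are also the efficacy outcome, so the table cannot by itself separate intolerance from lack of effect.

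Cost: protocol wording, a line or two on an existing form, one log, and slightly more data entry and tables. No added visits, participants or procedures.

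### Bowel habits are the only measure assigned to tolerability; nausea, vomiting, bloating and upper abdominal pain are listed drug effects scored in the diary but are not named as tolerability read-outs by dose

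*Combined protocol and SAP*

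**What the plan says.** Section II gives the reason for two doses: "participants will be randomized into high and low dose groups to assess for ideal dosing and tolerability". The same section sets the overall goal as choosing the more promising dose.

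Under (c) Study End Points, the measures are given these roles:

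- **mGCSI-DD (primary):** it "will be used as the primary instrument to assess for" efficacy. Its items are scored 0 to 5 and begin with "nausea, retching, vomiting, stomach fullness, ability to finish a normal-sized meal". Bloating and upper abdominal pain or discomfort come later in the list.
- **Breakthrough medication (secondary):** "Any change in frequency of use of breakthrough medications will be used as a secondary endpoint to assess for efficacy in the study".
- **Bowel habits (secondary):** "any significant change in bowel habits will help to assess for tolerability in this study". No other measure is linked to tolerability.

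Section VI says: "Known side effects of Senokot-S include diarrhea, nausea or vomiting, stomach pain, rectal bleeding, gas, abdominal bloating". Allergic reaction such as rash is also mentioned.

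Section V has the diary completed daily in a baseline week and then on sheets covering 28 days of treatment. At Visit 1 participants receive two relevant instructions: "They will be instructed to decrease use of any previously prescribed breakthrough medication as can safely be tolerated"; and "Subjects will be instructed to immediately contact the Principal Investigator if they experience episodes of significant diarrhea or rectal bleeding".

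Section XII describes all variables with standard summaries and compares pre and post outcomes for the two groups, without naming items. Section XIII assigns safety monitoring to the research office and the principal investigator, and allows stopping for a negative trend in diary scores, with no item, dose or threshold given.

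**The concern.** The study has to support a choice of dose, and tolerability is one of the two stated grounds for that choice. Several drug effects that the protocol itself lists are upper gastrointestinal. They will be recorded in the diary, but in an instrument whose only named uses are efficacy and an undefined stopping point. Someone following the text could therefore report tolerability by dose from bowel habits alone.

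Scoring these symptoms for efficacy is reasonable, because they are also symptoms of the disease. The difficulty is that they are not also shown separately by dose under a rule fixed in advance. If the diary is reduced to a total, a drug effect on one or two items can be cancelled by improvement on the others. If the items are looked at only after the results are known, the choice of items and of a worsening threshold is open. That matters more here because participants are told to cut back anti-emetics, prokinetics and analgesics, so these symptoms may well move.

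**Working it through.** The plan gives no figure on this point to reproduce. The core of it is a comparison of text; the arithmetic only illustrates what could be hidden and how much the remedy could show.

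**1. Side effects listed in section VI, set against the measures**

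| Listed effect | Where it is recorded | Role given in the plan |
|---|---|---|
| Diarrhea | Bowel habits form | Tolerability |
| Nausea or vomiting | mGCSI-DD: nausea, vomiting (retching is a related item) | Efficacy |
| Abdominal bloating | mGCSI-DD: bloating | Efficacy |
| Stomach pain | mGCSI-DD: upper abdominal pain or discomfort (close, not identical wording) | Efficacy |
| Rectal bleeding | Immediate-contact instruction | None stated |
| Gas, rash | No measure named | None stated |

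**2. Offset within a total score**

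Assumption, because there is no scoring rule: total = unweighted mean of the 10 listed items. If k items rise by 2 and the other 10 - k fall by 0.5, the change in the total is (2k - 0.5(10 - k))/10.

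- k = 1: (2 - 4.5)/10 = -0.25
- k = 2: (4 - 4)/10 = 0.00
- k = 3: (6 - 3.5)/10 = +0.25
- k = 4: (8 - 3)/10 = +0.50

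One item worsening is counted as improvement, and two are invisible. With three or four the total rises, but it does not show which symptom is responsible. If 6 of 30 in an arm have k = 1 and the other 24 fall by 0.5 on every item, the arm mean is (6 × (-0.25) + 24 × (-0.5))/30 = -0.45, against -0.50 with no one affected.

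**3. What a by-dose table could show**

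Inputs: 60 participants randomised 1:1, so about 30 per arm. Assumption: the mean of an item over one week varies independently from week to week with SD s = 0.4 to 0.6. The change from one baseline week to w treatment weeks then has SD s√(1 + 1/w). With w = 4 this is 0.447 to 0.671.

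- *Chance of a rise of at least 1 point with no true change:* 1.27% to 6.80% per item, or 0.38 to 2.04 of 30. With one week of treatment data it is 3.85% to 11.93%.
- *At least one of five items flagged by chance, items independent:* 1 - (1 - 0.0127)^5 = 6% to 1 - (1 - 0.0680)^5 = 30%. Positive correlation lowers this. For four items the figures are 5% to 25% if independent and 4% to 19% at correlation 0.5.
- *True sustained rise of 2:* flagged 93% to 99% of the time.
- *True sustained rise of 1:* flagged 50% of the time, because the cut sits at the mean.
- *Rise of 2 lasting one week of four (mean +0.5):* flagged 13% to 23%.
- *Precision:* 6/30 = 20% (exact 95% CI 7.7% to 38.6%). For 6/30 minus 3/30 the difference is +10 points (Newcombe 95% CI -8.8 to +28.5).

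The threshold count is thus a coarse measure. That is why the mean change with its CI should stand beside it, and why the dose contrast should be descriptive.

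**The case against.** The strongest reply is that section XII already covers this. It describes every variable and compares outcomes for the two groups, and each diary item is a recorded variable. That stands to this extent: the items are not excluded, and nothing confines the analysis to a total. A reader might infer that the plan will give no information on these symptoms by dose; the documents do not support that. What they support is that the items are not named as tolerability read-outs.

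A reader might also infer that drug-related worsening will in fact be masked. That too goes beyond the text. Masking requires a total score, which the protocol never specifies, and the example in the working is constructed. Analysis by item or subscale would reduce or remove it.

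Nor can one conclude that adverse events go unrecorded. Section XI lists no adverse-event form, but its list is not clearly exhaustive, section XIV binds the investigators to institutional reporting procedures that are not reproduced, and the consent pages are not available. The wording on bowel habits says only that they help to assess tolerability.

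It is also fair to say that the remedy is weak as a comparison and could be produced later from stored data. Both stand. They limit what the table can claim, but do not remove the value of fixing items and threshold before results are seen.

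**Conclusion.** The concern holds in limited form. Bowel habits are the only measure assigned to tolerability, although tolerability by dose is a stated purpose of the randomisation and three of the listed effects have close counterparts in the diary. This rests on the text alone.

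The possible offset (-0.25 for one item up 2 and nine down 0.5) depends on an assumed ten-item mean. The flagging rates depend on an assumed weekly SD of 0.4 to 0.6. Neither is needed for the main conclusion.

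The point is a minor to moderate improvement. It does not affect the primary analysis, and with about 30 per arm the added table would inform the choice of dose rather than settle it.

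**What to change.** In (c)b and XII, name nausea, retching, vomiting, bloating and upper abdominal pain or discomfort as descriptive tolerability read-outs by randomised dose. For each item report:

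- the mean change from the baseline week to the treatment period, with a 95% CI per arm and for high minus low;
- the number and percentage worsening by at least a prespecified amount. One point is a workable convention, but nothing in the documents validates it. Use the days completed for participants who stop early.

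Also report the number stopping early per arm. Make no hypothesis test. Show the table beside bowel habits and change in breakthrough medication when the dose is chosen.

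State the limits with it:

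- the dose contrast is imprecise;
- some flags arise by chance, more so for early stoppers and when several items are read together;
- a true 1-point rise is flagged only about half the time, and short-lived worsening is mostly missed;
- worsening may reflect the disease or the instructed cut in breakthrough medication, which may differ by dose;
- gas and rash are not covered.

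The cost is a few sentences and one table from data already collected, with no new visits or staff.
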